8.1 Disease State and Current Treatments

Migraine affects 14.7% of the world's population and is the most common neurological disease, characterized by recurrent debilitating attacks that can last from a few hours to several days. The primary symptoms are severe headache, nausea, vomiting and light/sound sensitivity. In some cases, attacks are triggered by hunger, stress, sleep disturbances, exercise, or by certain foods, drinks or drugs. For women, migraine attacks often occur in conjunction with their menstrual cycles.

Migraine with aura (MA) is a subset of migraine also known as classical migraine, comprising about a third of migraine patients (Launer et al., 1999; Russell et al., 1996). MA attacks are preceded or accompanied by so-called aura symptoms, most commonly visual disturbances, somatosensory disturbances and/or speech-related problems. Manifestations of visual auras can be numerous, e.g. zigzag lines. Somatosensory symptoms can be manifested as tingling or numbness.

Aura symptoms are thought to be caused by the phenomenon Cortical Spreading Depression (CSD).

Current acute treatments for MA include the so-called triptans (serotonin receptor agonists), overthe-counter pain-killers, opioids, anti-nausea medications, the recently approved so-called gepants (calcitonin gene related peptide (CGRP) receptor antagonists) and others. However, these medications are only moderately effective and often poorly tolerated, causing significant side effects and restricting use in many sub-groups (adolescents and children, pregnant and breast-feeding women, heart disease patients and more). Furthermore, too frequent use of migraine medications is a significant problem which often leads to a vicious cycle of medication overuse headache with headaches most days.

In a survey of more than 15,000 US migraine patients, 74% reported that they were not fully satisfied with their current acute treatment (Lipton et al., 2019).

A number of neurostimulation devices have been marketed for migraine but are not widely adopted or reimbursed, due to high prices, and (for many patients) side effects and limited effectiveness.

Consequently, there is a need for new, effective and affordable non-pharmaceutical migraine treatments.

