8.3 Intended Use and Population

The intended use application of the Rehaler is early treatment of acute attacks of migraine with aura in patients of ages 18+ to stop or alleviate migraine with aura attacks. The user breathes through the mouthpiece from the beginning of the aura symptoms until they disappear.

Migraine with aura is defined by the International Classification of Headache Disorders 3 (ICHD-3), category 1.2, according to the diagnostic criteria A to D below:

- A. At least two attacks fulfilling criteria B and C
- B. One or more of the following fully reversible aura symptoms:
 - visual
 - sensory
 - speech and/or language
 - motor
 - brainstem
 - retinal
- C. At least three of the following six characteristics:
 - at least one aura symptom spreads gradually over ≥5 minutes
 - two or more aura symptoms occur in succession
 - each individual aura symptom lasts 5-60 minutes
 - at least one aura symptom is unilateral
 - at least one aura symptom is positive
 - the aura is accompanied, or followed within 60 minutes, by headache
- D. Not better accounted for by another ICHD-3 diagnosis.

The study will include individuals aged 18 to 65, and exclude individuals with chronic pulmonary disease (e.g. COPD or pulmonary fibrosis), severe cardiovascular disease, cerebrovascular disease, anaemia, brain abnormalities, as well as pregnant women (see section 12).

[figure not shown]

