11.4.2 Stage 2 exploratory endpoints

1. Number of MA attacks during past month of Stage 2 and how many of these attacks were treated with the study device.

- Overall satisfaction with study device treatment effect in attacks treated in past month of Stage 2 (satisfaction measured on 5 point scale: 5 = Satisfied, 4 = Partially Satisfied, 3 = Neutral, 2 = Partially Unsatisfied, 1 = Unsatisfied)
- 3. How many times in the past month of Stage 2 has the participant taken respectively a prescription acute migraine drug, an over-the-counter acute analgesic or treated with a neurostimulator device, with the intention to treat migraine. Follow-up question: What was the type and dose of drug taken?
- 4. Proportion of participants who used an opioid drug to treat migraine during past month of Stage 2.
- 5. Proportion of participants who have been hospitalized for migraine during past month of Stage 2.
- Consistency of response among participants who treated three attacks or more during Stage
 2.

12 Study population

Participants who meet all the inclusion criteria and none of the exclusion criteria and who are willing and able to provide written informed consent, may be enrolled in the study. Participants may be recruited from patients followed at the study sites for their migraine, or from the general population by advertisements online and in newspapers, as well as informational brochures and posters.

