12.1.2 Exclusion criteria

Participants must meet none of the following criteria:

- 1. Participant has a history of chronic pulmonary disease (e.g. Chronic Obstructive Pulmonary Disease (COPD) or pulmonary fibrosis).
- 2. Participant has a history of severe cardiovascular disease (e.g. symptomatic coronary artery disease, prior myocardial infarction, congestive heart failure) or cerebrovascular disease (e.g. prior stroke or transient ischemic attack, symptomatic carotid artery disease, prior carotid endarterectomy or other vascular neck surgery).
- 3. Participant has a history of intracranial hyper/hypo-tension.
- 4. Participant has a history of cerebral aneurysm.
- 5. Participant has had previous brain surgery, including stenting.
- 6. Anaemia, defined as a hemoglobin concentration in capillary blood lower than 11 g/dL
- 7. Participant has a baseline S_{PO2} level which is lower than 95%
- 8. Participant has 15 or more headache days per month
- 9. Participant has medication-overuse headache (ICHD3 classification 8.2).
- 10. Participant has a known history or suspicion of recurring secondary headache which in the opinion of the investigator may interfere with the study.
- 11. Hemiplegic migraine
- 12. Participant has other significant and relevant pain problem (e.g. cancer pain, fibromyalgia or other head or facial pain disorders)
- 13. Participant has a known history or suspicion of substance abuse or addiction (within the last 5 years) that in the opinion of the investigator may confound the study assessments.
- 14. Participant has a history of psychiatric or cognitive disorder and/or behavioural problems which in the opinion of the investigator may interfere with the study.
- 15. Participant belongs to a vulnerable population or has any condition such that his or her ability to provide informed consent, comply with the follow-up requirements, or provide self-assessments is compromised (e.g. homeless, developmentally disabled, prisoner).
- 16. For female participants: is pregnant or actively trying to become pregnant.
- 17. Participant is participating in any other clinical investigation or has participated in an interventional clinical trial in the preceding 30 days.
- 18. Participant has any condition that according to the investigator may pose the participant at risk or provide confounding data.
- 19. Participant is unable, as perceived by study personnel, to correctly understand and follow the instructions for use of the device and ePRO app.

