13.2.1 Informed Consent

The potential participant is briefed by the PI or delegated study personnel (hereafter designated PI) about the study, including the study rationale, study plan, randomization to either study device or sham device, study design and possible side effects of the treatment. It is clearly explained to the patient that they may be assigned to either a functional (active) or non-functional (sham) device in Stage 1, that it is believed that the active device has the best treatment effect and that the participant is guaranteed to be assigned to this in Stage 2.

If the participant wishes, he/she can have up to a week to consider before deciding whether or not to participate (in that case, the visit will be stopped after Step 1 and resumed when the participant has decided).

A potential study participant considered for this study must be listed on a screening log to be maintained at the site. The PI must also enter in the participant's medical records that he/she is participating in the study. If the participant does not have a medical record at the study site, a new record must be started for him/her.

PI will instruct female participants of childbearing potential to practice effective contraception during their participation in the study.

13.2.2 Information to be recorded:

The following information is obtained and documented in the eCRF during Site Visit 1 (cf. document **PAREMA1 Case Report Form content**):

- General eligibility questions (e.g. age, headache frequency, current participation in other clinical investigations)
- Eligibility questions related to migraine with aura diagnosis (presence of aura symptoms, frequency of MA attacks, age at MA onset)
- Eligibility questions related to headache drug use and overuse
- Eligibility questions related to comorbidities (e.g. pulmonary, cardiovascular and cerebrovascular disease)
- Eligibility questions related to secondary headaches (e.g. caused by head/neck trauma or infection)
- Pulse oximeter test result (see section 13.2.3)
- Capillary blood test for anaemia
- For female patients:
 - Whether the patient has gone through menopause
 - \circ $\;$ If patient has not gone through menopause: urine pregnancy test $\;$
- Other eligibility questions, including participant's willingness to abide by study instructions, and ability and willingness to provide informed consent.
- Migraine without aura (MO) diagnosis and frequency

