Apart from CO_2 effects, the risk assessment must also address the issue of possible hypoxemia. Any partial rebreathing device without an external source of compressed oxygen gas will inevitably lead to a decrease in the inspired oxygen level. However, individuals conforming to the in/exclusion criteria (i.e. without pulmonary or cardiovascular disease or anaemia) have a significant extra-capacity for oxygen uptake, meaning that decreases in the inspired oxygen pressure from the normal sea level value of 21 kPa (dry basis) down to 16 kPa are unproblematic and do not lead to hypoxemia (West, 2008). This corresponds to the situation which arises when a person travels from sea level to a high altitude. Signs of oxygen inadequacies upon exertion typically do not manifest themselves below altitudes of approx. 2200 meters, where the oxygen partial pressure is 16 kPa. In the present case, where the device users will be sitting at rest while using the device, the potential for hypoxemia is even smaller. This is supported by the arterial blood data which showed a drop of C_{aO2} of less than 2%, as well as the pulse oximetry data showing that the $S_{pO2\%}$ range was the same (95%-100%) with the study device as at baseline (see section 8.5.1).

Use of the Rehaler is contraindicated for the following:

- Chronic pulmonary disease (e.g. Chronic Obstructive Pulmonary Disease (COPD) or pulmonary fibrosis)
- Severe cardiovascular disease (e.g. symptomatic coronary artery disease, prior myocardial infarction, congestive heart failure (CHF)
- Cerebrovascular disease (e.g. prior stroke or transient ischemic attack, symptomatic carotid artery disease, prior carotid endarterectomy or other vascular neck surgery)
- Anaemia
- Sickle Cell Disease
- Uncontrolled intracranial hyper/hypo-tension
- Past or present cerebral aneurysm
- Individuals with previous brain surgery, including stenting
- Use in airplanes or at altitude over 2000 meters (6600 feet) above sea level
- Pregnant or breastfeeding women
- Children under the age of 18

Rehaler has potential interactions when used in conjunction with the following pharmaceutical agents:

1. Anesthetic agents: interaction can give rise to cardiac dysrhythmias.

- 2. Neuromuscular blocking agents and hypotensive agents: the change in pH induced by Rehaler can influence uptake, distribution and action of drugs (including neuromuscular blocking agents, and hypotensive anesthetic agents).

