14.3 Benefit-Risk Analysis

Section 14.1 describes possible adverse device effects and risks pertaining to the clinical investigation. Based on that analysis, we believe that it is unlikely that the use of the investigational device or sham device will lead to serious adverse device effects.

As detailed in the Risk Management file and summarized in the Investigator's Brochure, relevant measures have been taken to mitigate residual risks.

Based on the data from the scientific literature, prior clinical studies of functionally equivalent versions of the device (the studies CapnoMigra, HVMASKE and EpiCapno), the extensive post-market safety data, and the mitigations applied to residual risks, we believe it will be safe to use the investigational device and the sham device in the clinical investigation, in the population defined by the in/exclusion criteria.

The study is intended to examine in a large-scale, randomized, controlled study whether it is possible to treat and prevent migraine with aura by using partial rebreathing. Such a study has not previously been reported in the literature and will provide valuable new knowledge about migraine and its treatment. In the light of the risk evaluation performed, it is our assessment that those potential benefits of the study outweigh the risks and possible discomforts that participants may experience during the study, and that the benefit-risk ratio of the clinical investigation is therefore acceptable.

Our group (sponsor and investigators) possesses the required expertise, experience, equipment and facilities to carry out the proposed study, as well as subsequently analyze and communicate the results in a peer-reviewed journal.

15 Adverse events and device deficiencies

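### The protocol contraindicates the device in breastfeeding women, but no eligibility criterion names breastfeeding

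*Protocol*

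**What the plan says.** Protocol section 14.1.1 gives a list of contraindications to the Rehaler. One entry is "Pregnant or breastfeeding women".

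The eligibility text is narrower. Exclusion 16 in section 12.1.2 reads "For female participants: is pregnant or actively trying to become pregnant". The population summary in section 8.3 ends its list of excluded conditions with "brain abnormalities, as well as pregnant women (see section 12". Inclusion 8 in section 12.1.1 asks female participants to use contraception and says nothing on breastfeeding. The Site Visit 1 items listed for women in section 13.2.2 are menopausal status and, where it applies, a test: "If patient has not gone through menopause: urine pregnancy test".

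Two further statements show how these criteria are used. Section 12 allows enrolment of "Participants who meet all the inclusion criteria and none of the exclusion criteria", given written consent. Section 14.3 concludes that it will be safe to use the devices "in the clinical investigation, in the population defined by the in/exclusion criteria".

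**The concern.** A contraindication protects a trial participant only if something in the enrolment process acts on it. Here the risk section names a group that should not use the device, while the list that decides who enters does not name that group. Exclusion 16 does not permit breastfeeding women; it is simply silent about them.

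Two things are at stake. First, a breastfeeding woman could be enrolled without breaching any named criterion. Randomization is 1:1, so she may receive the active device in Stage 1, and everyone who continues to Stage 2 receives five active devices. Second, section 14.3 ties its safety conclusion to a population whose named criteria do not keep out a group that section 14.1.1 contraindicates. The two sections do not agree.

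**Working it through.** No arithmetic beyond a count is needed. The check matches each contraindication in section 14.1.1 to the criteria in sections 12.1.1 and 12.1.2.

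**Counting the groups.** The list has 11 entries. One (aircraft and altitude) is a condition of use, not a patient characteristic, which leaves 11 − 1 = 10 patient-level entries. One of these names two groups (pregnant, breastfeeding), so there are 10 + 1 = 11 patient groups.

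**Matching them.**

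| Contraindicated group (14.1.1) | Named criterion |
|---|---|
| Chronic pulmonary disease | Exclusion 1 |
| Severe cardiovascular disease | Exclusion 2 |
| Cerebrovascular disease | Exclusion 2 |
| Intracranial hyper- or hypotension | Exclusion 3 (wider: any history, not only uncontrolled) |
| Cerebral aneurysm | Exclusion 4 |
| Brain surgery or stenting | Exclusion 5 |
| Anaemia | Exclusion 6 |
| Sickle cell disease | Exclusion 20 |
| Pregnancy | Exclusion 16 |
| Under 18 | Inclusion 3 |
| Breastfeeding | None |

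Ten of 11 groups are covered and one is not.

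**Could pregnancy be meant to include breastfeeding?** The wording does not support that. Section 14.1.1 names both. So does the background in section 8.1, which describes existing drugs as "restricting use in many sub-groups (adolescents and children, pregnant and breast-feeding women, heart disease patients and more". That sentence is not an eligibility rule and carries little weight, but it is the only other place where the protocol mentions breastfeeding, and there too it is named in addition to pregnancy.

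**Following the enrolment steps.** Online pre-screening (section 13.1.2) compares answers with the inclusion and exclusion criteria. At Site Visit 1 (section 13.2.7) eligibility is decided from a checklist and the investigator's evaluation. The protocol's items for women at that visit do not include breastfeeding, and a urine pregnancy test does not detect it. At each step the named criteria pass over a breastfeeding woman, and what remains is the investigator's judgement or material outside the documents.

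**The case against.** The strongest reply is that other safeguards exist. Exclusion 18 lets the investigator exclude anyone with "any condition that according to the investigator may pose the participant at risk", and site staff are trained on a protocol that contains the contraindication. Inclusion 10 requires agreement to use the device as intended, and contraindicated use arguably is not that. Section 8.5.4 shows that contraindications added after marketing went into the labelling and the Instructions for Use. Consent information is given before enrolment. The consent form, pre-screening questionnaire, case report form, Instructions for Use and label are not available, and any of them may mention breastfeeding.

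Part of this stands. A missing screening question has not been shown, only a missing named criterion. The population in section 14.3 is also shaped by exclusion 18 and inclusion 10, so the accurate statement is that breastfeeding women are not expressly excluded from it.

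The rest does not remove the gap. Exclusion 18 is discretionary and does not name the group. Inclusion 10 is an undertaking by the participant, not a check of status. The protocol did not leave the other ten groups to these general provisions. Even if the unseen materials do mention breastfeeding, the protocol's two lists still disagree.

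It is also fair to say that no harm is demonstrated: the protocol gives no reason why use while breastfeeding would be dangerous. That argues for a low rating, not for leaving the conflict in place. If the sponsor regards the contraindication as unnecessary, section 14.1.1 is the text to change.

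**Conclusion.** The point holds as a minor inconsistency bearing on participant safety. One of 11 contraindicated patient groups has no named eligibility criterion, and the enrolment rule as written can admit a woman for whom the protocol contraindicates the device.

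This rests on the protocol text alone. It assumes nothing about the consent form, case report form or Instructions for Use, which could reduce the practical risk. The number of women affected cannot be estimated from the documents. Nor do they show whether enrolment is still open; if it has closed, the correction protects fewer women, though the inconsistency remains.

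**What to change.** Amend exclusion 16 to read along the lines of *is pregnant, breastfeeding, or actively trying to become pregnant*, and make the matching edit in section 8.3. Add a question on breastfeeding at Site Visit 1 if the case report form lacks one. A single check at entry leaves later breastfeeding uncovered over participation of up to 27 months. The contraception requirement in inclusion 8 makes that unlikely, so repeating the question at Site Visit 2, before active devices are handed out, is a sensible option but not essential. If any breastfeeding women are already enrolled, the sponsor should state how they will be handled.

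The cost is one word in exclusion 16, one edit in section 8.3 and at most a question or two in the case report form. The change can go into the next amendment under section 20.2, where the sponsor must justify it and classify it as substantial or not. Version 3.2 of the protocol, which added sickle cell disease as an exclusion, is a direct precedent. Sample size, power and analysis do not change.

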14.1.2 Risks related to the sham device

The sham device has been altered so that participants breathe very low CO₂ concentrations when using it (cf. section 8.6 and Investigator's Brochure).

A series of technical tests with the sham device found that the inspired CO₂ percentage with the sham device was less than 0.1% and no clinically or statistically significant changes in ETCO2 occur during use.

There are therefore no known or suspected risks with the sham device.

14.2 Known Potential Benefits

Based on the migraine treatment results presented in section 8.5.3, we anticipate that the investigational (active) device will increase the likelihood of avoiding moderate or severe pain during migraine with aura attacks.

14.3 Benefit-Risk Analysis

Section 14.1 describes possible adverse device effects and risks pertaining to the clinical investigation. Based on that analysis, we believe that it is unlikely that the use of the investigational device or sham device will lead to serious adverse device effects.

As detailed in the Risk Management file and summarized in the Investigator's Brochure, relevant measures have been taken to mitigate residual risks.

Based on the data from the scientific literature, prior clinical studies of functionally equivalent versions of the device (the studies CapnoMigra, HVMASKE and EpiCapno), the extensive post-market safety data, and the mitigations applied to residual risks, we believe it will be safe to use the investigational device and the sham device in the clinical investigation, in the population defined by the in/exclusion criteria.

The study is intended to examine in a large-scale, randomized, controlled study whether it is possible to treat and prevent migraine with aura by using partial rebreathing. Such a study has not previously been reported in the literature and will provide valuable new knowledge about migraine and its treatment. In the light of the risk evaluation performed, it is our assessment that those potential benefits of the study outweigh the risks and possible discomforts that participants may experience during the study, and that the benefit-risk ratio of the clinical investigation is therefore acceptable.

Our group (sponsor and investigators) possesses the required expertise, experience, equipment and facilities to carry out the proposed study, as well as subsequently analyze and communicate the results in a peer-reviewed journal.

15 Adverse events and device deficiencies

